ALZUMAB™ should not be administered to patients having history of severe allergy or known hypersensitivity reaction to any component of ALZUMAB™ or any murine proteins. Additionally, ALZUMAB™ is contraindicated in patients with any active serious infection including tuberculosis and HIV-AIDS.

It is recommended that live/attenuated vaccines not be given concurrently with ALZUMAB™.

As with other IgG antibodies, itolizumab may cross the placenta during pregnancy. The available clinical experience is too limited to exclude a risk, and administration of ALZUMAB™ is therefore not recommended during pregnancy.

Infections and Reactivation of Tuberculosis

Physicians should exercise caution before and during Itolizumab Injection treatment in patients with a history of recurrent infections or underlying conditions which may predispose them to serious infections. Patients should be monitored closely for the development of signs and symptoms of infection during and after treatment with Itolizumab.

4. Objectives

Primary Objectives:

To study the efficacy and safety of adding Itolizumab in patients with Moderate to Severe COVID-19 complications (Cytokine Release Syndrome).

Secondary Objectives:

To study the effect of immunomodulation by Itolizumab and its correlation to clinical improvement by evaluating biomarker data (IL6, TNF-a, IL17, IL1, Interferon -A etc.) before and after Itolizumab treatment

5. Outcome Measures

Primary Outcome Measures:

1. Proportion of patients with deterioration of lung function as measured by*:
 - Stable SpO₂ without increasing FiO₂
 - Stable PaO₂ without increasing FiO₂
2. Reduction of endo-tracheal intubation rate, measured as rate of patients needing intubation*
3. Reduction in proportion of patients who need*
 - Non-invasive ventilation
 - Invasive mechanical ventilation
 - High flow nasal oxygen
4. Time of duration of mechanical ventilation or time to end of mechanical, measured as elapsed time from the start date of mechanical ventilation to the weaning date, for patients needing intubation*
5. One-month mortality rate between the two arms* [Time Frame: up to 1 month]

1-month mortality is defined as the ratio of patients who will live after 1month from study start out of those registered at baseline

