### **4.4 Exclusion Criteria**

1. Known severe allergic reactions to monoclonal antibodies
2. Active tuberculosis (TB) infection
3. History of inadequately treated tuberculosis or latent tuberculosis

Note: Latent tuberculosis should be excluded based on history, physical examination and chest x ray before dosing (day 1). QuantiFERON TB also should be performed, however considering criticality of patient condition, patient can be dosed without QuantiFERON TB test results. If

QuantiFERON TB test is positive, then continuation of patient in the study is investigator's discretion considering benefit-risk evaluation with the sponsor.

4. In the opinion of the investigator, progression to death is highly probable, irrespective of the provision of treatments
5. Patient on invasive mechanical ventilator support.
6. Have received oral anti-rejection or immune-suppressive drugs within the past 6 months  
Note: Patient receiving oral anti-rejection or immune-suppressive drugs regularly in the last 6 months will be excluded. Patient will be included if received short course of steroids.
7. Participating in other drug clinical trials like using anti-IL-6 therapy like tocilizumab (participation in COVID-19 anti-viral trials may be permitted if approved by Sponsor)
8. Patient on treatment of anti-IL-6 or plasma therapy as a part of supportive care
9. Pregnant or breastfeeding, or positive pregnancy test in a pre-dose examination
10. Any serious medical condition or abnormality of clinical laboratory tests that, in the investigator's judgment, precludes the patient's safe participation in and completion of the study
11. Patients with known history of Hepatitis B, Hepatitis C or HIV
12. Absolute Neutrophils count (ANC) <1000 / mm^3
13. Platelet count <50,000 / mm^3
14. Absolute Lymphocyte count (ALC): <500/mm^3

Note: ANC, ALC and platelet counts can be done in local lab in the hospital.

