## **9 Efficacy Evaluation**

### **Primary Efficacy Evaluation**

Proportion of patients with deterioration of lung function as measured by Stable SpO2 without increasing FiO2 and Stable PaO2 without increasing FiO2 will be summarized using count and

percentage. The difference between two proportion with its 95% Confidence interval and associated p-values may be presented, if p-value is less than 0.05 it can be concluded that there is a statistically significant difference between two proportions.

Reduction of endo-tracheal intubation rate, measured as rate of patients needing intubation will be summarize using descriptive statistics.

Reduction in proportion of patients who need/ Non-invasive ventilation / Invasive mechanical ventilation/high flow nasal oxygen will be summarized using count & percentage.

One-month mortality rate between the two arms will be summarized. The difference between two rates with its 95% Confidence interval and associated p-values may be presented, if p-value is less than 0.05 it can be concluded that there is a statistically significant difference between two-rates.

Change in inflammatory markers like CRP (C-reactive protein) level, d-Dimer, ferritin etc will be summarize with descriptive statistics. Change from Baseline may be presented along with 95% CI.

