### 14.2.3 Reduction in proportion of patients who need Non-invasive ventilation

Visit		Arm A (N=XX)	Arm B (N=XX)
	Patients on Non-invasive ventilation at baseline	XX	XX
Day 7	N	XX	XX
	Stable or improved (shifted to bag and mask, NRBM, FM, nasal canula or off O2)	XX (XX.X %)	XX (XX.X %)
Day 14	N	XX	XX
	Stable or improved (shifted to bag and mask, NRBM, FM, nasal canula or off O2)	XX (XX.X %)	XX (XX.X %)
Day 21	N	XX	XX
	Stable or improved (shifted to bag and mask, NRBM, FM, nasal canula or off O2)	XX (XX.X %)	XX (XX.X %)
Day 30/EOS	N	XX	XX
	Stable or improved (shifted to bag and mask, NRBM, FM, nasal canula or off O2)	XX (XX.X %)	XX (XX.X %)

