### 14.2.4 Reduction in proportion of patients who need NRBM

Visit		Arm A (N=XX)	Arm B (N=XX)
	Patients on NRBM at baseline	XX	XX
Day 7	N	XX	XX
	Stable or improved (shifted to FM, nasal canula or off O2)	XX (XX.X %)	XX (XX.X %)
Day 14	N	XX	XX
	Stable or improved (shifted to FM, nasal canula or off O2)	XX (XX.X %)	XX (XX.X %)
Day 21	N	XX	XX
	Stable or improved (shifted to FM, nasal canula or off O2)	XX (XX.X %)	XX (XX.X %)
Day 30/EOS	N	XX	XX
	Stable or improved (shifted to FM, nasal canula or off O2)	XX (XX.X %)	XX (XX.X %)

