### 14.2.6 Reduction in proportion of patients who need High Flow Nasal Oxygen

Visit		Arm A (N=XX)	Arm B (N=XX)
	Patients on High flow nasal oxygen at baseline	XX	XX
Day 7	N	XX	XX
	Stable or improved (off O2)	XX (XX.X %)	XX (XX.X %)
Day 14	N	XX	XX
	Stable or improved (off O2)	XX (XX.X %)	XX (XX.X %)
Day 21	N	XX	XX
	Stable or improved (off O2)	XX (XX.X %)	XX (XX.X %)
Day 30/EOS	N	XX	XX
	Stable or improved (off O2)	XX (XX.X %)	XX (XX.X %)

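### Primary endpoint 3 counts each breathing support separately with no rule for intubation or death, and the planned tables report a different quantity

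*SAP*

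**What the plan says.** Protocol section 5 and SAP 3.2.1 define the third primary outcome as "Reduction in proportion of patients who need" NIV, invasive mechanical ventilation or high flow nasal oxygen, set out as three separate bullets. SAP section 9 gives the whole analysis in one sentence: "Reduction in proportion of patients who need/ Non-invasive ventilation / Invasive mechanical ventilation/high flow nasal oxygen will be summarized using count & percentage". No test or confidence interval is attached. Neither document defines need, combines the three supports, or says what happens when a patient is intubated or dies without using a lesser support.

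SAP section 13 does have rules that carry forward the status of patients who worsen or die, but it limits them to the lung-function endpoint (primary endpoint 1).

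Exclusion 5 in SAP 4.4 keeps out any "Patient on invasive mechanical ventilator support", so every invasive ventilation is an event after entry. NIV and high flow are allowed at entry, and the shells expect them.

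The table shells describe another quantity. Table 14.2.3 is titled "Reduction in proportion of patients who need Non-invasive ventilation" but starts from "Patients on Non-invasive ventilation at baseline" and counts those stable or improved at each visit. Table 14.2.6 starts from "Patients on High flow nasal oxygen at baseline", and 14.2.4 from "Patients on NRBM at baseline". Table 14.2.5 does the same for face mask. Table 14.2.2 counts intubation over the whole arm.

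**The concern.** The shells treat a move from NIV to a mask, a cannula or no oxygen as improvement, and invasive ventilation is barred at entry. NIV therefore lies between mask oxygen and intubation. The documents do not rank high flow explicitly, but they list it with the other two as something to reduce.

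A middle step counted on its own can fall for two opposite reasons: patients did not worsen, or they worsened past it. Read literally, SAP section 9 cannot tell these apart. A patient intubated or dying straight from a mask never enters the NIV or high-flow count, and that moves both proportions in the direction labelled benefit. A treatment that holds patients on NIV or high flow who would otherwise have been intubated moves them the other way.

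Two of the three parts of a primary endpoint could then understate, overstate or reverse a real difference. In addition, if the tables are produced as drawn, the endpoint stated in section 9 is not reported for NIV or high flow at all.

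**Working it through.** **Inputs.** Planned size is about 30 at 2:1 (protocol section 6, SAP 4.5), so 30 × 2/3 = 20 in Arm A and 30 × 1/3 = 10 in Arm B. The plan has no formal sample size calculation and gives no rate for any support, so there is no figure to reproduce and every rate below is assumed.

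**General condition.** Let c be the proportion who reach NIV, high flow or invasive ventilation, and d the proportion intubated without passing through NIV or high flow. The proportion needing NIV or high flow is c - d. Its difference is

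(cA - cB) - (dA - dB).

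If Arm A is truly better (cA < cB), the sign reverses when dB - dA > cB - cA, that is, when the imbalance in direct intubation exceeds the benefit.

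**Worked range.** Take 8/20 (40%) v 6/10 (60%) escalating, a difference of -20 points, with nobody on NIV or high flow at baseline. One Arm A patient is intubated directly, so NIV/high-flow need in Arm A is 7/20 = 35%. Suppose k of the six in Arm B are intubated directly, and nobody on NIV or high flow is intubated later.

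| k | NIV/high flow, Arm B = (6 - k)/10 | A minus B (points) | Invasive ventilation, A v B |
|---|---|---|---|
| 0 | 60% | -25 | 5% v 0% |
| 1 | 50% | -15 | 5% v 10% |
| 2 | 40% | -5 | 5% v 20% |
| 3 | 30% | +5 | 5% v 30% |
| 4 | 20% | +15 | 5% v 40% |

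The cumulative count stays at 40% v 60% in every row. Reversal needs dB > 0.20 + 0.05 = 0.25, so at least 3 of the 6 escalating Arm B patients, against 1 of 8 in Arm A. The example pools NIV and high flow, which the plan counts separately.

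**Other assumed rates.** NIV/high-flow need is c × (1 - share intubated directly).

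- 40% v 60% escalating, 20% direct in both arms: 32% v 48%, no reversal.
- 40% v 60%, 10% v 30% direct: 36% v 42%, so a 20-point benefit shows as 6.
- 40% v 60%, 10% v 50% direct: 36% v 30%, reversed.
- 30% v 60%, 10% v 50% direct: 27% v 30%, no reversal.
- 50% v 60%, 10% v 30% direct: 45% v 42%, reversed. A smaller true benefit needs less imbalance.

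In simulation at 20 v 10 (400,000 runs per scenario), the chance that the observed cumulative count favours Arm A while NIV/high flow favours Arm B was:

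- about 4 to 7% with equal 20% direct shares (30 to 50% v 60% escalating);
- 32 to 41% with 10% v 50% direct (30 to 40% v 60% escalating);
- zero with no direct intubation.

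**The shells.** Suppose Arm B has 6 mask patients and 4 NIV/high-flow patients at baseline, with 3 of those 4 stable or improved and one intubation already counted. Sending 0 to 4 of the mask patients straight to intubation leaves the NIV/high-flow result at 3/4 = 75%. The mask result falls from 6/6 = 100% to 2/6 = 33%, and table 14.2.2 rises from 1/10 = 10% to 5/10 = 50%. The miscount does not arise there, but neither does a count of new NIV or high-flow use.

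**The case against.** A reader might infer that the planned tables will score a patient intubated from a mask as a success for NIV and for high flow. The documents do not support that. Shells 14.2.3 and 14.2.6 are confined to baseline users of each device, so the patient is in neither. That patient is a non-success in the mask tables and an event in table 14.2.2, and the SAP says the key content of the shells will not change. The miscount follows only from the section 9 wording, in which need is undefined.

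A reader might also infer that worsening would be hidden or that the sign would usually flip. Neither follows. Invasive ventilation is part of the same endpoint, intubation is primary endpoint 2, and table 14.2.7 gives mortality with an interval and p-value. Endpoint 3 carries no planned test, and reversal needs an imbalance larger than the benefit. An ordinal-scale summary is also planned (table 14.2.11), although the SAP does not define the scale.

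All of this stands and limits the point. It does not remove it. Shells that avoid the miscount by reporting another quantity do not deliver the stated endpoint. They also have no death rule: N is shown separately at each visit and SAP section 6 bases percentages on non-missing values, so a patient who dies could leave later denominators. Imbalance in the route to intubation is plausible, because the trial is open label, supportive care follows each institution's own protocol, and about 30 patients may come from up to 10 sites.

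**Conclusion.** The point holds in limited form. As worded in protocol section 5 and SAP section 9, the NIV and high-flow parts of primary endpoint 3 have no reliable favourable direction, because intubation or death without those supports lowers them. The invasive-ventilation part is not affected by direct intubation, though a death without intubation would lower it too. Separately, the shells and section 9 describe different quantities, and no table counts new NIV or high-flow use after baseline.

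In the worked range, a 20-point benefit appears as anything from 25 points better to 15 points worse. Distortion is the ordinary result, and reversal needs a strong imbalance, three or more direct intubations among six escalations in Arm B against one among eight in Arm A. These sizes rest wholly on assumed rates and on nobody using NIV or high flow at baseline. One patient is worth 1/10 = 10 points in Arm B. The change should be made. The trial's account of harm does not depend on this endpoint alone.

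**What to change.** In SAP section 9 and the 14.2 tables, with protocol section 5 aligned, define need and report two cumulative proportions by Day 30:

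1. high flow, NIV, invasive ventilation or death, among patients on neither high flow nor NIV at baseline;
2. invasive ventilation or death, among all patients.

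Give each with the between-arm difference and 95% CI. Both have one favourable direction, and neither requires ranking high flow against NIV. Keep the single-device counts and the baseline-device shells as description only, without calling a lower figure a reduction, and count deaths in those shells as not stable or improved.

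The cost is SAP wording, two table rows and an amendment to the protocol's outcome list. Changing the SAP alone would leave the two documents in conflict. SAP section 1 allows revision before database lock. Delivery mode, intubation dates and survival are already in Listings 16.1.12 and 16.1.17, and the shells already need the baseline device.

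The downside is that the first proportion leaves out patients already on high flow or NIV at entry. The documents do not give that share, and with about 10 patients in Arm B before any are removed, its interval will be wide.

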### **Secondary Efficacy Evaluation**

Biomarkers (IL-6, TNF-a, IL1, IL17, etc...) will be summarize using summary statistics.

Lymphocyte count will be summarized using count & percentage.

PaO2 (partial pressure of oxygen) / FiO2 (fraction of inspired oxygen, FiO2) ratio (or P/F ratio) calculated from arterial blood gas analyses. Radiological response will be summarized in descriptive manner.

Duration of hospitalization will be summarized using descriptive statistics.

Time to independence from non-invasive mechanical ventilation and from oxygen therapy will be summarize using summary statistics.

Biomarkers (IL-6, TNF-a, IL1, IL17, etc...) Lymphocyte count, CRP (C-reactive protein) level, PaO2 (partial pressure of oxygen) / FiO2 (fraction of inspired oxygen, FiO2) ratio (or P/F ratio), will be summarized with descriptive statistics. Change from Baseline will be presented along with 95% CI for the difference between two treatments will be reported.

Radiological response, Duration of hospitalization & Remission of respiratory symptoms will be summarized using descriptive statistics.

Number of participants with treatment-related side effects as assessed by Common Terminology Criteria for Adverse Event (CTCAE) version 5.0 graded according to CTCAE criteria (v5.0) will be summarized based on frequency and proportion of total subjects, by system organ class and preferred term. Proportion of subjects with IRR in both the arm will be presented. An overall summary of deaths will be presented by treatment arms.

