Source data is all information, original records of clinical findings, observations, or other activities in a clinical study necessary for the reconstruction and evaluation of the study. Source data are contained in source documents. Examples of these original documents, and data records include: hospital records, clinical and office charts, laboratory notes, memoranda, subject's diaries or evaluation checklists, pharmacy dispensing records, recorded data from automated instruments, copies or transcriptions certified after verification as being accurate and complete, microfiches, photographic negatives, microfilm or magnetic media, x-rays, subject files, and records kept at the pharmacy, at the laboratories, and at medico-technical departments involved in the clinical study.

Location of Data

All records and documents pertaining to the study will be maintained in the permanent files of the Investigator and will be available for inspection by the authorized party at any time.

Statistical Analysis

In general, continuous variables is summarized using descriptive statistics such as mean, standard deviation, 95% confidence interval (CI), minimum, and maximum. Categorical variables are summarized using proportions (counts and percentages). All statistical tests will be performed at 5% level of significance (two-sided test) and p-value<0.05 considered statistically significant (if necessary). All statistical analysis will be performed using SAS® (version 9.4 or higher) system software (SAS Institute Inc., USA)/or R/or EAST/or NCSS software.

11.Administrative Procedures

Ethics and Good Clinical Practice

This research will be carried out in accordance with the clinical research guidelines established by the basic principles defined in the revised New Drugs and Clinical Trials 2019, India and the principles enunciated in the Declaration of Helsinki [Ethical Principles for Medical Research Involving Human Subjects, revised, October 2013]. The investigator is responsible for overall activities at the center in accordance with Indian ICH-GCP guidelines, current New Drugs and Clinical Trials 2019 and ethical guidelines for biomedical research on human subjects issued by ICMR.

Interim study report - Data will be provided to DSMB (constituted prior to first patient screened) on a periodic basis. Based on DSMB recommendation, interim clinical study report may be prepared and submitted to DCGI/regulatory agencies.

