#### **4.5 Sample Size, Treatment Assignment, Randomization**

Approximately 30 patients are considered sufficient to explore the study objectives and will be included in this study (number of patients may be increased if there is benefit observed in initial cohort of patients. There is no formal sample size calculation estimated). All eligible patients entering into the study will be randomized in 2:1 ratio to receive the treatment A/ B respectively. A computer derived randomization schedule is planned to be generated using appropriate system e.g. SAS to assign patient to treatment groups. Randomization will be central and appropriate system (e.g. remote telephone based, computer-based email, sealed envelope) will be used to distribute randomization schedule to the site Note: If the patient is randomised to Arm A and is not initiated itolizumab or not administer one full infusion, is then not considered randomized. The same randomisation code will be used for the subsequent subject in that particular site.

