## **6 General Aspects for Statistical Methods**

In general, metric variables and derived parameters will be presented using descriptive summary statistics including arithmetic mean, standard deviation, median, minimum and maximum.

Categorical variables will be presented using descriptive summary statistics including number of patients and percentages. Percentages of patients will be based on non-missing values. The presentation will be by treatment group. Individual values as well as minimum and maximum will be presented with the same number of decimal places as the raw data. Derived parameter will have as many decimal places as the measured number with the smallest number of decimal places. Descriptive statistics, such as arithmetic/geometric mean and median will be presented with an additional decimal place and standard deviation with two additional decimal places as the raw or derived data. All relevant subject data will be included in the listings; and all subjects entered into the database will be included in subject data listings. SAS 9.4 or any other validated software will be used for analysis purpose and generating Tables, Listings & Figures. P-values less than 0.05 may be reported as statistically significant.

The formatting of the final version of a table, figure, or listing may differ from what is presented in the mock shell or the presentation of the results may be changed, however the key content will remain unchanged. Additional tables, figures, and listings may be generated to supplement the planned output.

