## **8 Demography other baseline Characteristics**

Demographic characteristics including age, gender, race, and ethnicity will be summarized for ITT/FAS populations. Baseline is defined as the last observed value/data before the patient receives study drug for the first time or randomized (in Arm B)

Vital signs such as height, weight, pulse, temperature, respiratory rate, systolic blood pressure, diastolic blood pressure, PaO2/FiO2, FiO2, SpO2, mean arterial pressure & GCS score will be summarized.

Medical history, Physical Examination & concomitant medications will be summarized using counts and percentage. Additionally, prognostic markers and few key laboratory parameters will be summarized.

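### Between-arm differences in change from baseline (SAP 9) lose precision without baseline adjustment and, for skewed markers, a log scale; their validity is not in question

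*SAP*

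**What the plan says.** SAP section 9, Secondary Efficacy Evaluation, lists biomarkers, lymphocyte count, CRP and PaO2/FiO2 and states "Change from Baseline will be presented along with 95% CI for the difference between two treatments will be reported". No model, covariate or transformation is attached to that interval.

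The scale has to be inferred from elsewhere:

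- SAP section 6 sets the default: "metric variables and derived parameters will be presented using descriptive summary statistics including arithmetic mean, standard deviation, median, minimum and maximum".
- Shells 14.1.7 to 14.1.9 show change from baseline as N, mean (SD), median, minimum and maximum.
- A geometric mean appears once, in a rule on decimal places ("Descriptive statistics, such as arithmetic/geometric mean and median will be presented with an additional decimal place"). It assigns no endpoint to the log scale.

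For the inflammatory markers under primary outcome 6, SAP section 9 is weaker: "Change from Baseline may be presented along with 95% CI". Shell 14.2.8 tabulates those markers before and after dosing in Arm A only.

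Baseline is defined for both arms. SAP section 8 says "Baseline is defined as the last observed value/data before the patient receives study drug for the first time", and for Arm B refers to randomization. Neither document mentions ANCOVA, a baseline covariate or a mixed model.

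**The concern.** A change score subtracts the whole baseline value, whatever its correlation with follow-up. When that correlation is modest this over-corrects, and chance baseline imbalance, which can be sizeable with about 10 controls, is carried into the estimate. ANCOVA estimates how much of the baseline to subtract.

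CRP and cytokines are also usually right-skewed, so a difference in arithmetic means can be dominated by a few patients. The documents give no distributions, so skewness is an assumption here.

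At stake is how much the between-arm intervals in SAP section 9 can say in a trial of about 30 patients whose baseline values are collected anyway.

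**Working it through.** **Inputs from the documents.** About 30 patients and 2:1 allocation (SAP 4.5), so about 20 v 10; two-sided 5% level (Protocol section 10, Statistical Analysis). The SAP states that no formal sample size was calculated, so there is no planned precision or power figure to reproduce.

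**Assumed.** Baseline-to-follow-up correlation (rho) 0.3 to 0.7; follow-up SD scaled to 1; lognormal markers with log SD 0.8 or 1.0 as main cases and 0.5 and 1.5 as extremes; no missing values.

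**Step 1: equal baseline and follow-up SD.** Let k = 1/20 + 1/10 = 0.15.

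- Change score: variance 2(1 − rho)k, t on 28 df.
- ANCOVA: variance (1 − rho²)k × 27/26, t on 27 df. The factor 27/26 = 1.038 is the average cost of estimating the baseline slope at N = 30.
- Variance ratio: (1 + rho)/2 × 27/26.

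| rho | Variance ratio | Half-width, change | Half-width, ANCOVA | Narrower by | Change-score N for equal precision |
|---|---|---|---|---|---|
| 0.3 | 0.675 | 0.939 | 0.773 | 17.7% | 44 |
| 0.5 | 0.779 | 0.793 | 0.701 | 11.6% | 39 |
| 0.7 | 0.883 | 0.615 | 0.578 | 5.9% | 34 |

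The last column is 30 divided by the variance ratio, rounded. Comparing follow-up values alone gives a half-width of 0.793, so at rho 0.3 the change score does worse than ignoring baseline. ANCOVA stays narrower until rho is about 0.92.

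**Step 2: unequal SDs.** If baseline SD is c times follow-up SD, the ratio becomes (1 − rho²)/(1 + c² − 2·rho·c) × 27/26.

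| c | rho 0.3 | rho 0.5 | rho 0.7 |
|---|---|---|---|
| 0.7 | 0.88 | 0.99 | 1.04 |
| 0.5 | 0.99 | 1.04 | 0.96 |

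For example, at c = 0.7 and rho 0.5: 0.75/0.79 × 1.038 = 0.99. The saving can shrink to nothing.

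**Step 3: skewed marker halved by treatment.** Simulated power at 20 v 10, for rho 0.3 / 0.5 / 0.7:

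| Analysis | Log SD 0.8 | Log SD 1.0 |
|---|---|---|
| Raw change | 0.27 / 0.34 / 0.45 | 0.178 / 0.204 / 0.282 |
| Log ANCOVA | 0.61 / 0.69 / 0.84 | 0.432 / 0.501 / 0.665 |

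Simulation error is at most about half a percentage point: sqrt(0.25/8,000) = 0.006 at log SD 0.8, and less at log SD 1.0 (20,000 trials). Over the same rho range, raw change v log ANCOVA is 0.62–0.88 v 0.94–1.00 at log SD 0.5 and 0.08–0.10 v 0.22–0.36 at log SD 1.5.

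**Step 4: source of the gain.** At log SD 1.0 and rho 0.7 the total gain is 0.665 − 0.282 = 0.383. Log change without adjustment reaches 0.614, which is 0.332 of that. Baseline adjustment on the raw scale reaches 0.504, which is 0.222. At rho 0.3 the order reverses: log change reaches 0.315 and raw ANCOVA 0.368, against 0.432 for both together.

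**Step 5: validity.** At log SD 0.8 to 1.0, with no effect or a halving, the raw between-arm 95% interval covers 93.2% to 95.8%. Null rejection for log ANCOVA is about 5%. For raw change it is 4.0% to 4.4% at log SD 1.0, slightly conservative.

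**The case against.** The strongest reply is that the plan is largely descriptive and does nothing invalid. SAP 4.5 says "Approximately 30 patients are considered sufficient to explore the study objectives", and the between-arm interval has close to nominal coverage. That stands: this is a point about efficiency.

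Several further objections also stand:

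- The SAP does not say that the contrast is an unadjusted arithmetic mean change. That is the plain reading of sections 6 and 9 with the shells, and nothing contradicts it, but it is an inference.
- Adjustment is not literally free. It costs 1 df and about 4% in variance, and the log scale changes the estimand.
- Entry on PaO2/FiO2, ferritin or IL-6 level (SAP 4.3) may compress baseline spread, which is the setting where Step 2 shows little or no gain.
- Cytokine sampling differs by arm (SAP 3.2.2), the number and interval of Arm A infusions vary, and early-discharged patients are followed by telephone. Some visits will therefore have few paired values.

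A reader might also infer that primary outcome 6 and the secondary objective rest on these contrasts. The documents do not support that. For outcome 6 the SAP plans descriptive statistics and an optional interval, and shell 14.2.8 covers Arm A only. Ferritin and d-Dimer are not in the between-arm list. The secondary objective concerns correlation of biomarkers with clinical improvement, which ANCOVA on treatment does not address.

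**Conclusion.** The point holds as an avoidable loss of precision. With equal SDs the between-arm interval could be about 6% to 18% narrower over rho 0.3 to 0.7. The gain may be nil if baseline SD is 0.5 to 0.7 of follow-up SD. For a lognormal marker halved by treatment, log-scale ANCOVA raises power substantially at log SD 0.8 and 1.0, and at rho 0.7 most of that comes from the log scale. All of these sizes depend on assumed SDs, correlations and distributions, and on complete data.

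A reader might go further and conclude that the planned intervals are wrong because the markers are skewed. The concern about skewness bites hardest on an interval for a single arm's mean, which is not the one promised for these variables. The between-arm interval covers 93% to 96% in the cases tried.

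Because baseline is already defined for both arms and the remedy is a wording change, the revision is worth making.

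**What to change.** In SAP section 9, Secondary Efficacy Evaluation, name the estimator:

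- At each time point sampled in both arms, estimate the between-arm difference by ANCOVA with treatment and the baseline value, with a 95% CI.
- Analyse CRP and cytokines on the log scale (outcome and baseline) and report the ratio of geometric means with 95% CI. Treat ferritin, d-Dimer and LDH the same way if they are compared between arms.
- State a rule for values below the assay limit.
- Analyse PaO2/FiO2 and lymphocyte count untransformed, with baseline adjustment.
- Keep the change-from-baseline tables as descriptive output.

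Cost: SAP wording and a few lines of code, with no new data. SAP section 1 allows revisions before database lock. The statistical price is 1 df, about 4% in variance, and a ratio-scale estimand for the logged markers. The change does not deal with values missing after death or discharge, or with the differing sampling schedules.
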